4.2.5 Sample size considerations

The feasibility count of 975,000 individuals gives an estimated mean of 108,000 per annum over the nine years of the study. Assuming an annual denominator population of 14 million (and hence prevalence of A&G of approximately 800/100,000), then per annum 95% confidence limits for the prevalence of A&G will be \pm 5/100,000. For assessing percentage of A&Gs which result in a referral, assuming an estimate of 50%, then per annum 95% confidence limits will be \pm 0.3% overall and \pm 3% for a lowest covariate (e.g., ethnicity group) category prevalence of 1%.

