4.2.7 Definition of the study population

All individuals in the CPRD Aurum database, regardless of age, with an A&G or referral recorded between 01/01/2015 to date of the most recent Aurum build (currently March 2024). For determination of incident A&G, they must have 24 months prior registration in CPRD Aurum or be aged 2 years or under. There is no comparison or control group.

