4.3 DATA / STATISTICAL ANALYSIS

We will determine the annual total number of A&G and total number of routine direct referrals from 2015 to 2023. Annual prevalence will then be defined as the total number of patients with i) an A&G and ii) a routine referral code recorded within each calendar year, divided by the total registered population at the start of each calendar year and expressed per 100,000 persons. Annual incidence will be defined (as in our previous incidence studies) as the total number of patients with i) A&G and ii) routine referral codes recorded within each calendar year who have no recorded A&G or routine referral codes in the previous 24 months, divided by the total registered population with at least 24 months registration at the start of each calendar year, and expressed per 100,000 persons. We will determine prevalence and incidence overall, and stratified by age and sex.

Patterns of A&G use (number, prevalence, incidence) will also be described across specialties and type of health condition, and by neighbourhood deprivation, ethnicity, CCG, and geographical region to assess if any change over time in consultation incidence and prevalence varies by these characteristics. We will produce caterpillar plots to show variation by geographical region and CCG. We will repeat for quarterly incidence and prevalence of A&G (up to date of most recent CPRD Aurum build). We will use joinpoint regression analysis and segmented regression on the annual and quarterly prevalence and incidence to determine impact of the COVID pandemic [2020/2021] and changes in policy on A&G.

Within those with A&G we will derive the percentage with a recorded referral in the 122 days (4 months) i) before and ii) after A&G record and compare these over time, and by the covariates (excluding those with less than four months of follow-up), descriptively and by using binary logistic regression. We will repeat for the sensitivity analysis of 12 months. We will descriptively compare trends in incidence and prevalence of A&G and routine direct referrals with publicly available data on trends on e-referrals from https://digital.nhs.uk/dashboards/ers-open-data which currently covers the period October 2019 to March 2024.

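### The WP1a incidence numerator and denominator follow different eligibility rules, for children under 2 and for people inside the 24-month wash-out

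*Protocol*

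**What the plan says.** Three statements in the protocol together define WP1a incidence.

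- **Who can be a case, by registration and age (section 4.2.7).** The study population is "All individuals in the CPRD Aurum database, regardless of age, with an A&G or referral recorded" in the study window. Then: "For determination of incident A&G, they must have 24 months prior registration in CPRD Aurum or be aged 2 years or under".
- **Who can be a case, by history (section 4.3).** Cases are patients with a code in the calendar year "who have no recorded A&G or routine referral codes in the previous 24 months".
- **Who is in the population (section 4.3).** The case count is "divided by the total registered population with at least 24 months registration at the start of each calendar year, and expressed per 100,000 persons". There is no exception for young children, and people with a recent code are not removed.

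Section 4.3 also promises: "We will determine prevalence and incidence overall, and stratified by age and sex". The same measures are repeated quarterly for A&G and feed joinpoint and segmented regression. Section 4.2.8 says only that age will be categorised and gives no bands. Section 4.3 notes that the incidence definition follows the team's earlier incidence studies. No other section reconciles the three statements.

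**The concern.** A rate is interpretable when everyone who can enter the numerator is also in the denominator, and everyone in the denominator could enter the numerator. The WP1a definition departs from this in both directions.

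- **(a) Cases outside the population.** A child under 2 on 1 January cannot have 24 months' registration on that date. Section 4.2.7 lets that child be an incident A&G case; section 4.3 leaves the child out of the denominator.
- **(b) Population not at risk.** A person with a recent code is inside the wash-out and cannot be incident until it has passed, yet section 4.3 counts that person for the whole year.

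Mismatch (a) acts on the youngest age stratum. Mismatch (b) is larger for the commoner pathway and grows with uptake, so it bears on the comparison of A&G with direct referral over time, which is the first aim in section 4.1.

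**Working it through.** **The plan's own figures.** The protocol gives no incidence figure, only precision for prevalence and for the percentage referred (section 4.2.5). These reproduce to its rounding:

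- Mean individuals per year: 975,000 / 9 = 108,333 (stated 108,000).
- Prevalence: 108,333 / 14,000,000 = 774 per 100,000 (stated approximately 800).
- 95% half-width: 1.96 × √(p(1−p)/14,000,000) = 4.6 to 4.7 per 100,000 (stated 5).
- Percentage referred: 1.96 × √(0.25/108,000) = 0.30%, and 1.96 × √(0.25/1,080) = 2.98% in a 1% category (stated 0.3% and 3%).

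None of them uses the incidence definition, so none is affected.

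**(a) Children under 2.** If a share u of the eligible population is under 2 and missing from the denominator, the overall rate is multiplied by 1/(1−u). The protocol does not give u. For an assumed 1.5% to 2.5%:

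- u = 0.015: 1/0.985 = 1.015
- u = 0.025: 1/0.975 = 1.026

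The overall overstatement is thus about 1.5% to 2.6%. Within the youngest stratum it depends on the band. Assume equal birth cohorts, a uniform rate, and children aged 2 and over registered from birth. A band of k single years then loses two of them:

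- Ages 0-4: 5/3 = 1.67, overstated by about 67%
- Ages 0-9: 10/8 = 1.25, overstated by 25%
- Ages 0-17: 18/16 = 1.125, overstated by 12.5%
- Under 2: cases over zero, undefined

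**(b) People inside the wash-out.** If a share q of the denominator is not at risk, the reported rate is (1−q) times the at-risk rate. With an annual probability a of a qualifying code and independent years:

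- Look-back counted from 1 January: q = 1−(1−a)².
- Look-back counted from the event date: codes before January block, on average over the year, 18 months' worth, so q ≈ 1−(1−a)^1.5.

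For A&G codes alone, a = 0.00774 from section 4.2.5. Then q = 1−0.99226² = 1.5% from 1 January, or 1−0.99226^1.5 = 1.2% from the event date. At three times that prevalence the first figure becomes 1−0.97679² = 4.6%.

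For routine referral, the protocol gives no rate, so a is assumed:

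| Assumed annual rate | From event date | From 1 January |
|---|---|---|
| 5% | 1−0.95^1.5 = 7% | 1−0.95² = 10% |
| 10% | 1−0.90^1.5 = 15% | 1−0.90² = 19% |
| 15% | 1−0.85^1.5 = 22% | 1−0.85² = 28% |

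The table applies to A&G incidence as well if a code of either kind breaks the clearance. The wording of section 4.3 can be read that way, or as the respective code for each pathway.

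**The case against.** The strongest reply is that WP1a is descriptive and hypothesis generating (section 4.2.1), that a registered population with a minimum look-back is a common simplification which the team has used before, and that the one error computable from protocol figures, A&G codes alone, is about 1.5%. This stands as an argument about importance. It does not remove the contradiction between sections 4.2.7 and 4.3 over young children, and precedent does not show that the convention is harmless here. It does little harm when events are rare and happen once, but section 4.2.3 reports 1.7 million requests for 975,000 people, about 1.74 each.

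That repeat use also counts against the sizes in (b). If the same people recur from year to year, the share inside the wash-out is smaller than under independence, so the table tends to overstate. In the other direction, the 975,000 are distinct people over nine years. Anyone with A&G in several years is counted once, so 0.77% may understate annual prevalence, and the 1.5% with it.

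Several stronger conclusions are tempting, and the protocol does not support them:

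- **That people with a code in the last 24 months cannot be cases at all that year.** Section 4.3 does not anchor the look-back. Counted from the event date, only those coded in the 12 months before 1 January are barred all year. Those last coded 12 to 24 months before can become cases later in the year.
- **That A&G incidence is wrong by 10% to 28%.** This needs an assumed referral rate, a look-back from 1 January, and the reading in which either code breaks the clearance.
- **That the youngest stratum is wrong by 67%.** This needs a 0-4 band, which the protocol does not specify.
- **That age gradients are flattened because referral is commonest at older ages.** The protocol gives no referral rates by age.

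The exception for age 2 or under is written for incident A&G only. Whether it extends to incident routine referral is unstated.

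**Conclusion.** The mismatch is real and lies in rules that the protocol itself fixes.

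- **(a)** overstates incidence by about 1.5% to 2.6% overall, on an assumed under-2 share of 1.5% to 2.5%. The larger effect is in the youngest stratum: 12.5% to 67% across the three illustrative bands, undefined for an under-2 band.
- **(b)** understates incidence by at most about 1.5% for A&G codes alone at the protocol's mean prevalence, growing with uptake. For routine referral, or for A&G if either code breaks the clearance, it is about 7%, 15% or 22% at assumed annual rates of 5%, 10% or 15%, and up to 10%, 19% or 28% if the look-back starts on 1 January. Repeat use in the same people would lower these.

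The two errors run in opposite directions and fall in different places, so a single caveat cannot cover both. A reader might infer that the WP1a results as a whole are unreliable. They are not: prevalence, counts, the percentage of A&G followed by referral, and the stated precision do not use this definition. No conclusion is shown to reverse. The definition should be corrected before incidence is computed, but it is not a reason to hold up the study.

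**What to change.** Rewrite the incidence definition in section 4.3 so that one rule governs both sides:

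1. Apply the exception for age 2 or under in numerator and denominator, or in neither, and say whether it covers routine referral as well as A&G.
2. State whether the 24-month clearance is pathway-specific (no prior A&G for incident A&G, no prior routine referral for incident referral) or broken by either code.
3. Use person-time at risk with the look-back counted from the event date. This also gives the right exposure to people who reach 24 months' registration during the year. If a head count on 1 January is kept, anchor the look-back to 1 January in numerator and denominator alike. Removing recently coded people from a 1 January head count while counting the look-back for cases from the event date would create a new mismatch, because people last coded 12 to 24 months earlier could be cases without being in the population.
4. Apply the same rule to the quarterly series; with a head count, anchor it to the start of each quarter.

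The cost is one revised definition and some programming. The registration dates and the 24-month code history are already needed to identify cases; the denominator must use them for the whole registered population.

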The Patient Association undertook work to explore the patient's voice. Unable to engage GP practices, patients were recruited through their own newsletter and stakeholder activities. Patients (n=8) with self-reported experience of A&G primarily reported a lack of shared decision-making and partnership working and a lack of effective communication during the referral process. Improvements suggested included establishing dialogue between patients, GPs, and specialists.¹⁰

A survey of Royal College of General Practitioners clinical advisors in 2022 showed that 91.7% of GPs use A&G, with 83% finding it useful. However, concerns were identified and escalated to the CQC and NHSE. Whilst secondary care waiting lists increased following the pandemic, the number of referrals to secondary care that were rejected also increased. This rejection does not end the need for patient care and more patients and carers were felt to be being 'held' in the community, increasing the pressure on, and creating a backlog, in primary care. The RCGP reported that A&G is being used by some providers to manage waiting lists (as a tool to convert referrals to A&G or using A&G to decline referrals) to the detriment of patients and primary care.

A further survey of 366 GPs, published in Pulse Magazine in early 2023, reported that 68% felt A&G was blocking necessary referrals. 78% felt that A&G was increasing their workload, 60% felt that A&G was requiring them to work beyond their competence, and 68% reported that patients were complaining because their wish to see a specialist had been diverted. ¹² SCSs report the challenges of providing useful advice based upon limited A&G referral information, such as being asked to interpret results of investigations in the absence of relevant clinical history and/or findings and patients report being unfamiliar with referrals process and disenfranchised from A&G pathways.

Literature demonstrates that A&G can be efficient and effective in particular settings, that key aspects for service development include an understanding of suitable cases, collaborative working across the health system, consideration of resource implications, and that existing A&G services may still yield high outpatient appointments with relatively few requests ending with expedited patient journeys (e.g., investigation requests and direct advice). The evidence to date has set the scene for effective use of A&G but flagged how use varies across specialties.

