4.1 OBJECTIVES, SPECIFIC AIMS & RATIONALE

The objective of this sub-study is to determine the extent of variation in use of Advice and Guidance (A&G) in primary care. The specific aims are to determine:

1) if use of A&G has increased over time in comparison to direct referrals

NIHR 158681BADGER			
Protocol Version 2.0 18/06/2024	CPMS: 58336	IRAS No: 333799	CPRD ID: 24_004022

- 2) variation in use of A&G by socio-demographic characteristics
- 3) which specialties and health conditions have higher rates of A&G
- 4) the percentage of A&G which end up with a direct referral.

This study is the first part of a programme of work which has the overall aim to understand whether A&G reduces waiting times and access to specialist care as planned, without making the quality of patient care worse. This initial study will examine changes in use of A&G over time and how it varies by sociodemographic characteristics and specialty.

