To derive the comparative prevalence and incidence of elective referrals, direct routine referrals will be determined using codes with a term indicating a referral and defined by consensus of study team to indicate a routine referral to a specialty (i.e. not fast track or referral with an intention to admit / emergency referral). To ascertain A&G events which result in a direct referral, we will determine

NIHR 158681BADGER			
Protocol Version 2.0 18/06/2024	CPMS: 58336	IRAS No: 333799	CPRD ID: 24_004022

referrals within 122 days (4 months) after date of an A&G request. These will be defined as i) a direct referral code defined as above and by ii) linking events in the Referrals table to the Observation table and determining duration of time between the linked observation event and the A&G request date. We will also determine referrals within 122 days (4 months) before an A&G request to see how often A&G requests follow a referral request. As a sensitivity analysis we will repeat for 365 days (12 months) either side of the A&G request date. Code lists for A&G have been derived and used in our CPRD feasibility study (FS_002830). The draft code list for direct referral has also been developed. These code lists are included in the appendix.

Covariates:

- 1) Age at date of A&G request (categorised)
- 2) Sex
- 3) Geographical region
- 4) CCG pseudonym
- 5) Ethnicity group
- 6) Deprivation (based on IMD quintiles)

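### Aim 4 pools A&Gs with and without a recent prior referral, so a change in that mix could look like a change in conversion to referral

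*Protocol*

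**What the plan says.** Protocol section 4.1 states aim 4 as "the percentage of A&G which end up with a direct referral".

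Section 4.2.8 defines the outcome as "referrals within 122 days (4 months) after date of an A&G request". It adds a second measure: "We will also determine referrals within 122 days (4 months) before an A&G request to see how often A&G requests follow a referral request". The sensitivity analysis keeps the same structure with a longer window: "As a sensitivity analysis we will repeat for 365 days (12 months) either side of the A&G request date".

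Section 4.3 takes everyone with an A&G as the base and sets the two percentages: "we will derive the percentage with a recorded referral in the 122 days (4 months) i) before and ii) after A&G record". These are compared over time and by the covariates. The only exclusion and the model are given together: "excluding those with less than four months of follow-up), descriptively and by using binary logistic regression".

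The covariates listed in section 4.2.8 are age, sex, region, CCG, ethnicity and deprivation. Prior referral is not among them. Nothing in section 4.2.8 or 4.3 restricts, stratifies or adjusts the after percentage by the before indicator, or tabulates one against the other.

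**The concern.** An A&G requested when no referral is on record and an A&G requested after a referral are different starting points. In the second case a later referral code may be absent because the earlier referral still stands, or present because a declined referral was sent again. The conversion percentage in that group therefore need not equal the percentage among A&Gs with no recent referral.

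The Protocol itself expects the second group, since it plans to count it. Section 1.1.2 also makes a changing mix plausible. It reports that rejected referrals rose after the pandemic, and that some providers use A&G "as a tool to convert referrals to A&G or using A&G to decline referrals". If that practice differs by year or place, the share of A&Gs that follow a referral may differ along the axes on which the after percentage is to be compared, namely time, region and CCG. The logistic regression could then show a trend or a locality difference in conversion when neither group's own conversion had changed.

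**Working it through.** **Inputs from the Protocol.** Section 4.2.5: about 108,000 individuals a year, 50% assumed for the overall percentage of A&Gs resulting in a referral, and a smallest covariate category of 1%. The share with a referral in the prior 122 days and the conversion percentage in that group are not given anywhere, so every value of them below is an assumption.

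**1. The plan's precision.** Half-width = 1.96 × √(p(1−p)/n), with p = 0.5.
- n = 108,000: 0.298 points (stated ±0.3).
- n = 1,080: 2.98 points (stated ±3).

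Both reproduce. The 108,000 counts people, not A&G requests.

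**2. What the pooled figure contains.** Let b be the share with a prior referral, c0 the after percentage without one, and c1 the after percentage with one.

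Pooled = (1−b)·c0 + b·c1 = c0 + b·(c1−c0)

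The shift from c0 is b·(c1−c0). It is zero if c1 = c0, negative if c1 < c0 and positive if c1 > c0. With c0 = 50% for illustration (an assumption, because the Protocol's 50% is the pooled value):

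| b | c1 = 0% | c1 = 25% | c1 = 50% | c1 = 70% |
|---|---|---|---|---|
| 5% | 47.5% | 48.8% | 50% | 51% |
| 10% | 45% | 47.5% | 50% | 52% |
| 20% | 40% | 45% | 50% | 54% |
| 30% | 35% | 42.5% | 50% | 56% |

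**3. Effect of a change in mix alone.** With c0 and c1 fixed, the pooled figure moves by (b₂−b₁)·(c1−c0). For b rising from 5% to 20%:
- c1 = 0%: 0.15 × (−50) = −7.5 points
- c1 = 25%: 0.15 × (−25) = −3.75 points
- c1 = 50%: 0
- c1 = 70%: 0.15 × 20 = +3 points

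**4. Can the two planned percentages be used to recover c0?** Rearranging, c0 = (pooled − b·c1)/(1−b), with c1 anywhere from 0 to 100%. Take the Protocol's 50% as the pooled value, which is what it is.
- b = 10%: c0 lies between (50−10)/90 = 44.4% and 50/90 = 55.6%.
- b = 20%: c0 lies between (50−20)/80 = 37.5% and 50/80 = 62.5%.

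The two marginal percentages only bound c0. The cross-table identifies it.

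**5. Precision after splitting, at p = 0.5.**
- Without a prior referral, b = 5%: n = 102,600, ±0.31 points.
- Without a prior referral, b = 30%: n = 75,600, ±0.36 points, and ±3.6 for a 1% category.
- With a prior referral, b = 30%: n = 32,400, 0.98/√32,400 = ±0.54 points.
- With a prior referral, b = 5%: n = 5,400, 0.98/√5,400 = ±1.33 points.

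**The case against.** The strongest reply is that the analysis does what aim 4 says. The aim is a percentage of A&Gs and section 4.3 computes one, in a study that sections 4.2.1 and 4.3.1 call descriptive and hypothesis generating. The plan does not overlook prior referrals either: their percentage is reported at 122 and 365 days and compared over time and by covariates. A reader would therefore see any drift in the mix beside the conversion trend. A cross-table is also the sort of detail that a statistical analysis plan may add, and that plan is not at hand.

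Much of this stands. There is no contradiction between the aim and the analysis, and the size of the prior-referral group will be visible. What does not stand is that this is enough: step 4 shows that the two percentages cannot separate the groups. Nor is the matter simply left open, because section 4.3 itself fixes the base, the exclusion, the windows, the model and the comparisons.

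A reader might infer more than the documents support, in three ways.
- That patients already referred are counted as A&Gs that avoided a referral, so the figure is too low. The Protocol uses no such label. A repeated or re-coded referral in the after window counts as a conversion, so the shift may go either way or be nil.
- That section 1.1.2 shows the group to be large. It reports a practice of some providers. The Protocol does not say whether a referral converted by the provider produces an A&G code in the primary care record.
- That A&Gs with a prior referral should be removed from the aim 4 estimate. Any routine referral in the window counts, and no match on specialty is stated. Exclusion would also drop A&Gs for unrelated problems, more so at 365 days.

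**Conclusion.** The point holds as one of interpretability. The aim 4 percentage and its regression pool two groups that the plan already identifies but does not separate, so a change in their mix cannot be told apart from a change in conversion.

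The direction and size cannot be derived from the Protocol. The shifts shown, from 7.5 points down to 3 points up when the share rises from 5% to 20%, rest wholly on assumed values of the share and of both conversion percentages. They show only that modest mixing could exceed a half-width of 0.3 points. They are not estimates of bias, and if the two rates are equal the pooled figure is undistorted. The change is worth making because it is cheap and bears directly on a named aim; the planned overall percentage remains valid as a description.

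**What to change.** In section 4.3, cross-classify referral before (yes/no) by referral after (yes/no). Report the after percentage, its time trend and its logistic regression separately for A&Gs with and without a referral in the preceding 122 days, using 365 days in the sensitivity analysis. Alternatively, enter prior referral in the model as a stratum or as an interaction with time and the covariates. Keep the planned overall percentage alongside and do not replace it.

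State in the text that prior referrals are not matched on specialty, so some will concern another problem.

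The cost is one table and one indicator built from variables already planned. Intervals widen slightly for A&Gs without a prior referral (about ±0.36 instead of ±0.30 points a year if 30% had one). They are wider in the smaller group with a prior referral, most of all for rare covariate categories.

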4.3.2 Plans for addressing missing data

We will assume that if no code for A&G or referral is entered, it did not occur. It is possible the quality of recording has improved in recent years and will discuss this as a limitation in dissemination, but we do not expect bias in recording by the covariates. Not everyone will have an ethnicity recorded, and we will use a "Not recorded" category.

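### WP1a's four-month follow-up rule fits the 122-day look-forward but not the look-back, and the 12-month repeat does not say which cut-off it uses

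*Protocol*

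**What the plan says.** Protocol section 4.2.8 sets the look-forward as "referrals within 122 days (4 months) after date of an A&G request". It adds a look-back: "We will also determine referrals within 122 days (4 months) before an A&G request to see how often A&G requests follow a referral request". It then extends both: "As a sensitivity analysis we will repeat for 365 days (12 months) either side of the A&G request date".

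Section 4.3 puts both directions into one analysis: "Within those with A&G we will derive the percentage with a recorded referral in the 122 days (4 months) i) before and ii) after" the A&G record. These percentages are compared over time and by covariate, subject to one exclusion: "excluding those with less than four months of follow-up), descriptively and by using binary logistic regression". The longer window gets a single line: "We will repeat for the sensitivity analysis of 12 months". That line neither restates nor changes the exclusion.

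Two other passages decide what happens to a patient whose window is only partly observed:

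- Section 4.2.7 requires earlier registration for one purpose only: "For determination of incident A&G, they must have 24 months prior registration in CPRD Aurum or be aged 2 years or under".
- Section 4.3.2 settles absent codes: "We will assume that if no code for A&G or referral is entered, it did not occur".

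**The concern.** A percentage of patients with an event in a window can be read directly only if the whole window was observed for everyone in the denominator. Follow-up after the A&G shows that the period after it was observed. It says nothing about the period before.

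For the look-back, the stated rule therefore fails in two ways. It admits patients who joined the practice days or weeks before the A&G; if no referral code falls in that short stretch, they count as not previously referred. It also removes recent A&Gs, and patients who left or died within four months, although their look-back may be complete.

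For the 12-month look-forward, the text does not settle whether the cut-off lengthens with the window. If it does not, late A&Gs stay in the denominator before their later referrals can be seen, and the last year of the trend drops for that reason alone. Two analysts could follow the same sentence and report materially different 2023 results.

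**Working it through.** **1. The plan's own precision (section 4.2.5).** 975,000 individuals over nine years is 108,333 a year, given as 108,000. The half-width is 1.96 × √(0.5 × 0.5 / n). With n = 108,000 it is 0.298%; with n = 1,080 (a 1% category) it is 2.98%. The stated ±0.3% and ±3% reproduce and are not in dispute. They are the yardstick for the shifts below.

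**2. Does the rule fit each window?**

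| Analysis | Observation needed | Observation required by 4.3 | Fit |
|---|---|---|---|
| 122 days after | 122 days after A&G | four months after | yes |
| 122 days before | 122 days before A&G | four months after | no |
| 365 days after | 365 days after A&G | not restated | unclear |
| 365 days before | 365 days before A&G | follow-up only, length not restated | no, whichever length is meant |

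The 24-month registration rule does not close the look-back gap. It is limited to incident A&G, while these percentages are taken among all patients with A&G.

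**3. Size of the look-back effect (assumptions, not document figures).** Let r be the share of patients who register newly each year, spread evenly, and w the window in days. The share of A&Gs with an incomplete look-back is about r × w/365. If referrals are even over the window, an incomplete window is on average half observed. The relative understatement is then about half that share.

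- w = 122: r = 8% gives 2.7% incomplete and 1.3% understatement; r = 25% gives 8.4% and 4.2%.
- w = 365: r = 8% gives 8% incomplete and 4% understatement; r = 25% gives 25% and 12.5%.

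At an illustrative true value of 50%, the 122-day figure would read 50 × (1 − 0.013) = 49.3% to 50 × (1 − 0.042) = 47.9%.

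**4. Complete look-backs dropped by the rule.** Section 4.2.7 gives the build as March 2024 without a day, so 1 and 31 March are used as the range. The last 2023 date with 122 days of follow-up is 31 October or 30 November, which leaves 304 or 334 days. The rule therefore removes 61 or 31 of the 365 dates (17% or 8%) from an analysis that needs no follow-up.

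**5. The 12-month look-forward if the four-month cut-off is kept.** Assume A&G dates spread evenly over 2023.

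- Data to 31 March 2024: 334 dates retained, 91 with 365 days (to 1 April 2023). Incomplete: 243/334 = 73%.
- Data to 1 March 2024: 304 dates retained, 61 with 365 days (to 2 March 2023). Incomplete: 243/304 = 80%.

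The observed 2023 percentage is 50% × (complete dates + 243 × m) / retained dates. Here m is the mean share of 12-month referrals already seen among incomplete dates, whose follow-up runs from 122 to 364 days (mean 243).

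- Referrals even over 365 days: m = 243/365 = 0.666; observed 36.6% to 37.8%.
- Half by day 122, the rest even: m = 0.5 + 0.5 × 121/243 = 0.749; observed 40.0% to 40.9%.
- 80% by day 122, the rest even: m = 0.8 + 0.2 × 121/243 = 0.900; observed 46.0% to 46.3%.

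The shortfall from 50% is about 4 to 13 points, against a planned half-width of 0.3.

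**6. The same look-forward with a matching 365-day cut-off.** Eligible 2023 dates fall to 61 or 91, so 83% or 75% of 2023 leaves the analysis and the truncation just described disappears. Loss through deregistration or death is not modelled in any step.

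**The case against.** The strongest reply is that the main analysis is sound. Aim 4 in section 4.1 is the share of A&Gs that end in a direct referral, which is a look-forward, and its 122-day exclusion matches its window. A reader might infer from the shared exclusion that Aim 4 as a whole is biased downward. The document does not support that: any such bias is confined to the 12-month version, and only on one reading. This part of the reply stands.

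Second, repeating the analysis for 12 months can naturally mean that window and cut-off move together. Nothing says four months is kept, so a reader who takes the truncation as the stated plan goes too far. It is an ambiguity. Section 4.2.7 also allows a later build: data running to 30 December 2024 or beyond would give every 2023 A&G 365 calendar days. Both points stand, and they make step 5 conditional. Neither helps the look-back, because no length of follow-up shows earlier observation.

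Third, the look-back effect is modest and its size is assumed. A reader might also infer false variation by age, ethnicity, deprivation or locality. The protocol gives no registration turnover by group, so a differential effect is possible where turnover differs but is not shown.

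Fourth, registration filters are often left to a statistical analysis plan, WP1a is descriptive and exploratory, and one common rule keeps a common denominator for 'before' and 'after'. But the protocol did write a rule here, and it does not fit the look-back. Elsewhere it does ask for prior registration when looking back: for incidence (sections 4.2.7 and 4.3) and for the 24-month exposure window in WP2 (section 5.2.7). A common denominator would need both conditions, not follow-up alone.

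**Conclusion.** The point holds for the look-back, at both 122 and 365 days. Section 4.3 requires time after the A&G for a percentage that depends on time before it, and section 4.3.2 turns unobserved time into no referral. The direction is downward. The size cannot be fixed from the protocol: about 1% to 4% relative at 122 days and 4% to 12% at 365 days, if 8% to 25% of patients register newly each year and referrals are even over the window. The rule also discards A&Gs with a complete look-back.

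The 122-day look-forward is correctly specified and should be left alone.

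The 12-month look-forward is an ambiguity to close. If the four-month cut-off were kept with a March 2024 build and even dates, 73% to 80% of retained 2023 A&Gs would be incompletely observed. The 2023 figure would then show a spurious fall of about 4 to 13 points from an assumed true 50%, depending on referral timing. That would affect the last year of a sensitivity analysis, where it could be mistaken for a real change or for disagreement with the main result.

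The correction is worth making: the look-back fault needs no interpretation, and the remedy is small.

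**What to change.** In section 4.3, replace the single exclusion with one per direction and window:

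- **Before:** at least 122 days (365 for the sensitivity analysis) of registration before the A&G date, or registration since birth for infants younger than the window. No follow-up requirement. The infant exception is needed because the population has no age limit, and it parallels the exception for young children in section 4.2.7.
- **After:** at least 122 days (365 for the sensitivity analysis) of follow-up after the A&G date. The 12-month 'after' trend then ends at A&Gs dated 365 days before the end of data.

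The cost is a sentence or two of text and two filters in the code. Recent registrants leave the look-back. With the March 2024 build, 75% to 83% of 2023 dates leave the 12-month look-forward; those A&Gs could not have been fully observed in any case, and a later build would recover them. The 'before' and 'after' percentages will have different denominators, so each should be reported with its own count.
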